Procedures for Subjects to Request Withdrawal

Subjects who desire to discontinue participation in this study will contact the study coordinator via telephone or email to withdraw.

The information collected prior to subject withdrawal may be used if deemed necessary to complete the study. As an FDA regulated study, the data cannot be destroyed. Data will not be distributed to anyone.

Procedures for Investigator to Withdraw Subjects

The investigator will withdraw subjects who fail to complete the baseline or follow-up evaluation, or who report serious side effects of the study medication as determined by Co-I [name] [name]. (attending MS neurologist).

The information collected prior to subject withdrawal may be used if deemed necessary to complete the study, unless the subject informs us in writing that they withdraw the data collected and the samples collected. Previously collected data can only be withdrawn if it has not yet been de-identified and distributed.

Participants Will Be Recruited Yes

Recruitment Method(s) Clinical Practice

How Participants Will Be Identified

Patients meeting inclusion criteria for age and MS diagnosis will be as asked by their treating physician, nurse practitioner, or neuropsychologist if they would be interested in hearing more about the study. If the patient is interested in participating and reports subjective difficulty with memory, a member of the research team will either speak with them in person, or they will be asked if they want to be contacted by a member of the research team at another time, or they will be given contact information for a member of the research team. If the patient is interested and would prefer to be contacted, the clinician will provide us with the name and best way to contact them. We also have a list of patients who have asked us to contact them if we have any enrolling research studies. We will contact those patients at their preferred contact.

Who Will Initially Approach Member of Primary Care Team, Treating

Potential Participants Physician
How Research Will Be Introduced to Participants

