After informed consent, subjects will engage in a 30-minute screening consisting of memory tests (Rey Auditory Verbal Learning Test, Visual Reproduction of the Wechsler Memory Scale, Fourth Edition), word-reading test (Weschler Test of Adult Reading), depressive symptoms (Beck Depression Inventory, Fast Screen), and assessment of suicidal ideation within the past twelve months (Columbia Suicide Severity Rating Scale).

Patients who meet all inclusion criteria will advance to the fourteen week crossover trial.

- 1. Baseline Evaluation:
- a. Memory Tests: Selective Reminding Test, Brief Visuospatial Memory Test, Revised, CANTAB Paired Associate Learning, NIH Toolbox Picture Sequence Memory Test (PSMT)
- b. Cognitive Efficiency Tests: Symbol Digit Modalities Test, CANTAB Rapid Visual Information Processing, Woodcock Johnson Reading Fluency, WAIS-IV Digit Span
- c. Questionnaires: Perceived Deficits Questionnaire (self-report of cognitive/memory deficits), Beck Depression Inventory, Fast Screen (mood), Fatigue Severity Scale (fatigue), Columbia Suicide Severity Rating Scale (suicidal ideation)
- d. Motor Tasks: 25-foot walk, Nine Hole Peg Test

2. Phase One Drug:

Patients will receive atomoxetine or identically encapsulated placebo from the research pharmacy. They will receive two containers: one containing seven 40mg capsules, and one containing enough 80mg capsules for the remaining five weeks. Subjects will be instructed to take the 40mg dose once per day (in the morning) for the first seven days, and then switch to the 80mg dose once per day (in the morning) for the remainder of Phase One. Subjects will be encouraged to set an alert in their smartphones to remind them to take the capsule at the same time each day. Subjects will also be provided with information about atomoxetine (Strattera) provided by the pharmaceutical company (Eli Lilly). Patients will be instructed not to take more than one capsule per day. If they miss a dose, they should keep it in the container. All remaining capsules will be returned to the investigator at the end of the six weeks (when the subject returns for the first follow-up). Patients will also be instructed to contact the study team immediately if they experience any side effects.

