Data will be stored in a locked filing cabinet located in a locked closet, within a locked office (PI: [name]). Each lock has a separate key. Only two persons have the key to the filing cabinet: [name] (PI) and the study research coordinators. Data files will be kept separate from identifiable data (PHI), with the exception of a password protected and encrypted Excel file linking subject names and subject numbers. This file will be located on a ISMMS network drive and only accessed from ISMMS computers. Only [name] and the coordinators will have the password. Raw data files may be retrieved by [name] or the research coordinator, and viewed on site in a private office space. Files will not be removed from Mount Sinai Hospital. Files will be immediately returned to their secure location within the filing cabinet.

Power Analysis/Data Analysis Plan (Including Any Statistical Procedures)

[name] will lead statistical analyses, which will consist of dependent T-tests comparing differences in outcomes (e.g., memory composite score) between the drug and placebo phases of the cross-over trial.

20. Data - Safety Monitoring

More Than the Minimum Data Yes Safety Monitoring Will Be Done

Principal Monitor [name]

Additional Monitors

Specific Items That Will Be Monitored for Safety

Suicidal ideation will be monitored with the Columbia Suicide Severity Rating Scale. Subjects who report suicidal ideation at any point in the study will be escorted to the psychiatric emergency department at Mount Sinai Hospital for further evaluation.

Suicidal ideation and other adverse events reported by patients will be recorded. Co-I [name] [name]. will review all adverse events as they are reported, and judge severity. [name] is not involved in data collection or processing, so she can be unblinded to identify whether adverse events occurred during atomoxetine or placebo.

Frequency of Data Review

Suicidal ideation will be evaluated at baseline, first follow-up, and second follow-up for all subjects, and immediate action will be taken if suicidal ideation is present (as noted above).

[name] will also be told immediately of any other serious adverse events, such as allergy to atomoxetine. She will have access to condition assignments in the case of adverse events.

Rules for Alteration of Study Design

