After twelve subjects have been completed the trial, [name] will evaluate whether serious adverse events are more likely during atomoxetine or placebo. If serious adverse events are 2:1 more likely during atomoxetine, the study will be halted.

Selection Procedures to Minimize Toxicity

We are using the recommended dosage of atomoxetine based on prescribing information in the package insert. Also, we are excluding patients taking strong CYP2D6 inhibitors (e.g., paroxetine, fluoxetine, quinidine), which minimizes risk of toxicity.

Grading System to Evaluate Adverse Events

Serious adverse events will include suicidal ideation and allergy to atomoxetine.

Other adverse events include constipation, upset stomach, difficulty sleeping, dry mouth, loss of appetite, irregular periods, decrease in sexual function, urinary hesitancy sweating, and dizziness.

Procedures to Assure Data Accuracy

All adverse events reported to the research team at any time in the study (including the three assessment phases) will be recorded for frequency and severity. Severity will be judged my our study physician, [name] [name]. These will be documented in a study RedCap database, and will be reported for each condition (atomoxetine, placebo) with the study results. [name] will also be able to determine subject condition in the event of serious adverse events.

Suspension Reported to

Suspension would be reported the the IRB.

Anticipated Circumstances of Subject Withdrawal

Subjects would be withdrawn from the study if they experience any severe adverse events. Of course, subjects may choose to withdraw at any time without penalty.

Primary or Secondary Safety Endpoints

Primary safety outcome will be suicidal ideation.

Secondary safety endpoints include constipation, upset stomach, difficulty sleeping, dry mouth, loss of appetite, irregular periods, decrease in sexual function, urinary hesitancy sweating, dizziness, and allergy to atomoxetine.

Data Monitoring Committee Description

DMC.docx

DMC Charter Available

21. Funding

Funding Source Name National Multiple Sclerosis Society

Contact

Funding Category Foundation

Meditrack (https://contracts.tractmanager.com/Contracts/Login.aspx)

Grant or Contract Title Pilot Randomized Controlled Trial of Atomoxetine to Treat Memory Impairment in MS

Patients

Grant or Contract

Number

PP-1606-24739

Funding Status Funded **Project Initiated By** Investigator

Grant / Contract Principal [name]

Investigator (PI)

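### The trial-level safety look is timed by twelve completers, so withdrawals for harm among early entrants push it later; count withdrawn subjects towards the twelve (minor)

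*Combined protocol and SAP*

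**What the plan says.** Under Rules for Alteration of Study Design in section 20 (Data - Safety Monitoring), one evaluation takes place "After twelve subjects have been completed the trial". The criterion is: "If serious adverse events are 2:1 more likely during atomoxetine, the study will be halted".

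Two other places say who leaves the trial early:

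- Section 20, Anticipated Circumstances of Subject Withdrawal: "Subjects would be withdrawn from the study if they experience any severe adverse events".
- Section 9, Procedures for Investigator to Withdraw Subjects: the investigator withdraws those "who report serious side effects of the study medication as determined by Co-I".

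Detection of events is described in sections 10 and 20. For side effects, "Patients will also be instructed to contact the study team immediately if they experience any side effects". For the main serious event, "Suicidal ideation will be evaluated at baseline, first follow-up, and second follow-up for all subjects". The stated response is that "Subjects who report suicidal ideation at any point in the study will be escorted to the psychiatric emergency department"; withdrawal after ideation is implied rather than written.

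Section 20 also has the study physician review each adverse event as it is reported, and "She will have access to condition assignments in the case of adverse events". A Data Monitoring Committee file is attached, but its content is not in the public text.

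**The concern.** The check is started by a count of subjects who finish. The plan's own withdrawal rules take subjects with serious harm out of that count. The more often harm removes early entrants, the longer it takes to reach twelve completers, and the more subjects are enrolled before anyone applies the 2:1 criterion. The timing thus responds to harm in the wrong direction.

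At stake is the date of the only trial-level stopping criterion visible in the documents, in a trial of 24 subjects where each extra entrant is about 4% of the sample (1/24). The immediate handling of an individual subject's event is not at stake.

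**Working it through.** The plan gives no derivation for the number twelve and no expected event rates, so there is no figure of its own to reproduce.

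**Inputs from the protocol:** 24 subjects (section 10); enrolment over one year and 14 weeks per subject, as six weeks, a two-week washout and six weeks (section 9); trigger of 12 completers (section 20).

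**Assumptions:** subject k enters at week 52k/24; half are in each sequence; there is no replacement; an event in phase one leads to withdrawal at the week 6 visit. The per-phase risks pA (atomoxetine) and pB (placebo) are assumed values.

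**Step 1, no withdrawals.** The twelfth subject enters at week 12 × 52/24 = 26 and completes at week 26 + 14 = 40. Enrolled by then: 40 × 24/52 = 18.5, so 18 subjects.

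**Step 2, one withdrawal.** If one of the first twelve is withdrawn, the thirteenth entrant must complete instead. The check moves by 52/24 = 2.2 weeks, with about one more subject enrolled. A withdrawal among entrants too late to count towards the twelve changes nothing.

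**Step 3, expected delay.** Half the subjects take atomoxetine first, so the chance of completing is s = 1 - (pA + pB)/2. Expected extra entrants are 12/s - 12, and the delay is that number × 52/24. The weeks and enrolment in the last two columns come from 60,000 simulated trials per setting.

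| pA / pB | s | Extra entrants | Delay (weeks) | Current trigger: week, enrolled | Completed or withdrawn: week, enrolled |
|---|---|---|---|---|---|
| 2% / 2% | 0.980 | 0.24 | 0.5 | 40.5, 18.2 | 39.8, 17.9 |
| 5% / 5% | 0.950 | 0.63 | 1.4 | 41.4, 18.6 | 39.6, 17.8 |
| 20% / 5% | 0.875 | 1.71 | 3.7 | 43.7, 19.7 | 39.0, 17.5 |
| 30% / 5% | 0.825 | 2.55 | 5.5 | 45.5, 20.5 | 38.6, 17.3 |

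In the last two rows, all 24 are enrolled before the current check in about 1-5% of trials, and in none under the changed trigger.

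**Step 4, if 30 are randomised** (the number in section 7). The interval is 52/30 = 1.73 weeks, and with no withdrawals the check falls at 12 × 1.73 + 14 = week 34.8. At 20-30% against 5% it falls at weeks 37.8-39.2, a delay of 3.0-4.4 weeks.

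**Step 5, upper bound.** If every phase-two event also prevented completion, s = (1 - pA)(1 - pB). With 24 subjects the check then falls at weeks 41.1-42.8 for equal 2-5%, and at about weeks 48-53 for 20-30% against 5%.

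**Step 6, does the changed trigger weaken the rule?** I simulated 100,000 trials with phase-one withdrawals, counting events in all enrolled subjects with onset by the check, and halting if atomoxetine events are at least one and at least twice the placebo events. At 20% against 5%, halting is 80% under the current trigger and 79% under the changed one. At equal 10% risk, chance halting is 34% and 35%. Exposure at the check, at 20% against 5%, falls from 187 to 163 subject-weeks (84 atomoxetine, 79 placebo).

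**The case against.** **The effect is small at plausible risks.** This stands. At equal 2-5% the slip is at most about 1.4 weeks and 0.6 of a subject. The larger figures need atomoxetine risks that the documents do not suggest; subjects with ideation in the past twelve months or known hypersensitivity are excluded.

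**An unblinded physician already sees each event.** This also stands in part: a growing imbalance could be noticed before the formal check. But that review carries no written criterion for stopping the trial. The unseen committee file may contain one, so the point can speak only of the visible text.

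**Completers have taken both conditions, so counting them keeps exposure comparable.** This is a fair reason for the present wording. Under the changed trigger, however, exposure remains nearly balanced (84 and 79 subject-weeks).

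**Detection does not improve.** True; the gain is in timing only.

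A reader might go further in two ways that the documents do not support:

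- One could infer that withdrawn subjects' events are left out of the 2:1 comparison. Halting at 20% against 5% would then drop from 80% to 66%. But nothing limits the tally to completers, and section 20 records all reported adverse events by condition.
- One could infer that harm might prevent the check altogether. At 40% against 5%, the chance that 24 subjects yield fewer than twelve completers is P(Binomial(24, 0.775) ≤ 11) = 0.07%. It reaches 18%, P(Binomial(24, 0.57) ≤ 11), only if every phase-two event prevents completion. Ideation found at the second follow-up comes when dosing has ended, so that is a bound and not an estimate.

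**Conclusion.** The point holds as a minor one. The trigger and the withdrawal rules together make the visible halting check later when early entrants are withdrawn for harm, by about 2.2 weeks and one more subject enrolled for each withdrawal that affects the first twelve completions. Expected delay is 0.5-1.4 weeks at equal 2-5% risks, and about 4-5.5 weeks with about 2-2.5 more subjects enrolled at 20-30% against 5%.

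These sizes rest on assumed risks, even accrual of 24 subjects over 52 weeks, and withdrawal for phase-one events only. The weeks of delay shrink if 30 are randomised; section 21 says the sample was lowered from 30 to 24, and the documents do not say whether the 30 in section 7 allows for screening failures. The direction of the effect does not depend on these assumptions. It would be wrong to conclude that individual subjects are unprotected, or that no other stopping criterion exists.

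**What to change.** Reword section 20 so that the evaluation takes place when twelve randomised subjects have completed or been withdrawn. Add one clause confirming that serious adverse events in all randomised subjects, withdrawn ones included, are counted under the condition taken at onset. Check that the attached committee document agrees.

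The change needs wording only: no extra visits, subjects or procedures. It costs 24 subject-weeks of exposure at the check (187 - 163, at 20% against 5%), with halting by counts essentially unchanged. It does not make the check early: about 17 to 18 of 24 subjects are still enrolled by then.

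Keep the comparison by counts. A comparison of event rates per exposure can be shown alongside, but it should not replace the counts without discussion. Under the changed trigger it lowers halting at 20% against 5% from 79% to 72%, while reducing chance halting at equal 10% from 35% to 29%. That is a trade-off for the investigators to weigh.

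### One of the two serious events named for the 2:1 halting comparison is worded as allergy to the active drug, so the drug:placebo comparison can tilt towards a halt

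*Combined protocol and SAP*

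**What the plan says.** All the relevant text is in section 20 (Data - Safety Monitoring) of the combined protocol and SAP.

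- Rules for Alteration of Study Design sets one look, "After twelve subjects have been completed the trial", and the rule: "If serious adverse events are 2:1 more likely during atomoxetine, the study will be halted". It states no minimum number of events and no convention for zero placebo events.
- Grading System to Evaluate Adverse Events names two events: "Serious adverse events will include suicidal ideation and allergy to atomoxetine".
- Frequency of Data Review uses the same wording. The monitoring physician "will also be told immediately of any other serious adverse events, such as allergy to atomoxetine".
- Specific Items That Will Be Monitored for Safety says that this physician reviews all adverse events and judges their severity. She takes no part in data collection or processing, "so she can be unblinded to identify whether adverse events occurred during atomoxetine or placebo".
- Procedures to Assure Data Accuracy has every adverse event that reaches the team recorded, whenever it arises, with how often it occurred and how severe it was. It adds that events "will be reported for each condition (atomoxetine, placebo) with the study results".

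No treatment-neutral allergic-reaction term is defined, and nothing says whether an event is classified before or after its condition is looked up.

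**The concern.** A ratio of events on drug to events on placebo is interpretable only if the same event can be scored in either condition. Suicidal ideation meets that test, because the same scale is used at both follow-ups. The second named event carries the name of the active drug. A similar rash or reaction during placebo would be logged as an adverse event, but on a literal reading it is not an allergy to atomoxetine and need not be called serious. The physician who judges it may know that the patient was on placebo, which makes the literal reading easier to apply.

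Two things are at stake. The first is the halting decision, where counts will be small and a single event can decide the ratio. The second is the serious-event comparison reported with the results, which would carry the same asymmetry into planning for a possible phase 3 trial.

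**Working it through.** The plan gives no event rate, error rate or halting probability, so there is no figure of its own to reproduce. The two illustrations below isolate the effect of the naming. They take a reaction that is equally likely in either phase and compare scoring it wherever it falls (neutral) with scoring it on the atomoxetine side only.

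**Inputs from the plan.** The ratio is 2:1, the look is after 12 completers, and each patient has one six-week period on each condition.

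**Assumptions.** Ideation is equally likely in either phase. The rule is met when the drug count D is at least 1 and D ≥ 2 × P, where P is the placebo count.

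**A. Fixed number of events.** Let k ideation events split between phases as Binomial(k, 0.5), and add one reaction.

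- Neutral: all k + 1 events split as Binomial(k + 1, 0.5).
- Drug-only: D is 1 plus a Binomial(k, 0.5) count, and P is the remaining ideation events.

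For k = 2, neutral scoring splits three events, and the rule is met when D is 2 or 3: (3 + 1)/8 = 50%. Under drug-only scoring, with X ideation events on drug, the rule needs 1 + X ≥ 2(2 − X), so X ≥ 1: (2 + 1)/4 = 75%.

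| Ideation events k | Neutral | Drug-only |
|---|---|---|
| 0 | 50% | 100% |
| 1 | 25% | 50% |
| 2 | 50% | 75% |
| 3 | 31% | 50% |
| 4 | 19% | 31% |
| 5 | 34% | 50% |
| 6 | 23% | 34% |

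Comparing no allergy with one drug-phase allergy would be the wrong contrast (for example 25% v 75% at k = 2). It mixes the effect of the name with the effect of an additional event.

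**B. Assumed risks, 12 patients per condition.** Let p be the ideation risk per period and q the reaction risk per period. A patient's risk of a counted event is r = 1 − (1 − p)(1 − q) where reactions count, and p where they do not. D and P are taken as independent binomials with n = 12, and the probabilities are summed over all pairs that meet the rule. Neutral scoring uses r on both sides; drug-only uses r on atomoxetine and p on placebo. With p = 0.02 and q = 0.02, r = 1 − 0.98 × 0.98 = 0.0396.

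| q (p = 0.02) | Neutral | Drug-only | Difference |
|---|---|---|---|
| 0.01 | 0.224 | 0.248 | 0.024 |
| 0.02 | 0.261 | 0.317 | 0.056 |
| 0.05 | 0.320 | 0.490 | 0.170 |

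If the rule is read strictly (D > 2 × P), the pairs are 0.213 v 0.240, 0.240 v 0.304 and 0.261 v 0.461, in the same direction.

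**Sensitivity.** If placebo reactions are a quarter as common as drug reactions, the neutral figures rise to 0.242, 0.302 and 0.443. The drug-only figures do not change, so the gaps fall to 0.006, 0.015 and 0.047.

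**The case against.** The strongest reply is that the plan never excludes a placebo-phase reaction. All reported adverse events are recorded throughout and reported by condition. A natural sequence is that a suspected allergy is reported under the blind and its condition looked up afterwards. The wording of both passages also leaves the list open: one says what serious events will include, the other gives allergy as an example. This stands. A reader might infer that such an event cannot be recorded under placebo, and the documents do not support that. What they leave open is whether it would be classed as serious and so enter the ratio.

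A reader might also infer a contradiction because the secondary safety endpoints end with "urinary hesitancy sweating, dizziness, and allergy to atomoxetine". There is none. Seriousness and endpoint rank are different classifications, and suicidal ideation is likewise both a serious event and a safety endpoint.

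Three further replies have some force.

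- A genuine drug allergy ought to count against the drug. Under a neutral name it still does.
- Allergies may be rare, since section 8 excludes known hypersensitivity to atomoxetine, and the effect is small when placebo reactions are much rarer than drug reactions. Both limit the size.
- The rule is unstable anyway: with no minimum count and no allergies at all, the chance of halting under equal 2% ideation risk is already 0.173. That is a separate weakness, and the wording adds to it.

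The Data Monitoring Committee document is named only as an attachment and may deal with classification. Its content is not available here.

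**Conclusion.** The point holds in a limited form. As worded, one of the two named serious events can be read as scorable on atomoxetine only, and the severity judgement may be made with the condition known. The serious-event ratio can therefore be tilted towards halting. How far depends on how placebo-phase reactions are classified, which the plan leaves to judgement.

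Under the stated assumptions, drug-only scoring of one reaction raises the chance of meeting 2:1 by 11 to 50 percentage points across zero to six ideation events. With 12 patients per condition and 2% ideation risk, it adds 0.024 to 0.170 to the chance of halting for reaction risks of 1% to 5%, and less if placebo reactions are rarer. These rates are assumptions, and the figures for zero placebo events also rest on treating 1:0 as meeting the rule. The work shows that wording could change the outcome; it does not show that the trial would be wrongly halted.

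**What to change.** Reconcile the wording under Frequency of Data Review and Grading System to Evaluate Adverse Events so that the allergic event has a treatment-neutral name, for example allergic reaction to study capsule. State that each such event, in either phase, is classified as serious or not before its condition is revealed, and that the by-condition safety report uses the same definition. If the monitoring committee document already says this, a cross-reference is enough.

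The 2:1 ratio and the decision to halt stay with the sponsor and monitor; nothing here proposes a different threshold. The cost is one event definition, one case-report item and one sentence on the order of classification and unblinding. No extra visits, patients or data are needed.
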